- A 6-point composite endpoint of CV death, non-fatal MI, non-fatal stroke, hospitalization for unstable angina, coronary revascularization or hospitalization for heart failure
- Individual events including all-cause mortality, CV death, fatal and non-fatal MI, fatal and non-fatal stroke, hospitalization for unstable angina, hospitalization for CHF, or coronary revascularization. Both first events and total events, taking account of repeat events will be examined
- Change in eGFR from baseline
- Change in UACR from baseline
- Incidence of adverse events of interest. Adverse events of interest including urinary tract infections including urosepsis and pyelonephritis, genital mycotic infections, diuretic effects including hypovolemia, hypotension episodes, hypoglycemia, hepatotoxicity, falls and fractures, malignancies, hypersensitivity reactions, acid-base disorders, renal failure events, and amputations

Other safety assessments:

- Adverse events
- Clinical laboratory events
- Physical examinations
- Vital signs including orthostatic blood pressure
- Use of concomitant medications

Statistical Methods:

The primary endpoint is the difference in the change in HbA1c from week 0 (randomization visit) to week 24 among subjects exposed to bexagliflozin, 20 mg, compared to subjects exposed to placebo. Statistical significance will be declared at a two-sided 0.05 level of significance. The intention-to-treat population that includes all randomized subjects regardless of treatment adherence or availability of follow-up data will be analyzed. A mixed model repeated measures (MMRM) analysis of covariance model (ANCOVA) with baseline HbA1c as a covariate will be performed on the available data, incorporating all visits from

each patient at which HbA1c was measured.

Three key secondary endpoints are:

1. Change in HbA1c from baseline to week 24 in randomized subjects who have been prescribed insulin to control their diabetes
2. Change in body weight from baseline to week 48 in subjects with a BMI ≥ 25 kg/m²
3. Change in SBP from baseline to week 24 in subjects with baseline systolic blood pressure ≥ 140 mmHg

A hierarchical testing strategy in the following order will be undertaken, if the null hypothesis is excluded for the primary efficacy endpoint:

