3.2.2 Treatment Period

The treatment period for each study subject will start at randomization. Randomization will be stratified by baseline HbA1c ($>$ or $\leq 9.5\%$), baseline estimated glomerular filtration rate (eGFR) ($<$ or ≥ 60 mL/min/1.73m²), baseline BMI ($<$ or ≥ 25 kg/m²) and history of heart failure. The study subjects will be in contact with the study site at 2, 6, 12, 18, 24, 36 and 48 weeks post-randomization. The interactions at week 2 and week 18 will be conducted by phone unless a clinic visit is necessary. After week 48, clinic visits will be scheduled every 24 weeks and a phone interview will be conducted at 12 weeks after each clinic visit. The treatment period will vary from subject to subject and will end for all subjects after the last randomized subject has completed at least 52 weeks of treatment and a total of 134 subjects have experienced a MACE+. It is anticipated that subjects will receive treatment for 2 to 3 years. A follow-up visit will take place 4 weeks after the conclusion of treatment.

At the start of the treatment period each subject will be provided investigational product, dosing instructions, and a glycemic control diary in which to record glucose measurements obtained through self-monitored blood glucose (SMBG) testing. Information related to the occurrence of hyperglycemic or hypoglycemic events as well as symptoms that may suggest ketoacidosis will be recorded. The subjects will be instructed to take the investigational product with water in the morning prior to eating. Additional medications for hyperglycemia and for control of other medical conditions will be allowed if deemed medically necessary by the investigator, and will be recorded ([Section 5.2.5](#) and [Section 5.6](#)).

During the first 24 weeks of the treatment period, hyperglycemia should be managed with diet and exercise counseling and only with changes in the medical therapy if the investigator feels it is necessary for the well-being of the subject. Intensification of the antidiabetic regimen should adhere to the following guidelines upon the report by a study subject of two fasting blood glucose self-measurements exceeding the following values on consecutive

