9.5 Primary Endpoints

9.5.1 Primary Efficacy Endpoint

The primary efficacy hypothesis is that bexagliflozin reduces HbA1c after 24 weeks of treatment when compared to placebo. The primary efficacy analysis on change in HbA1c at week 24 is based on the ITT using all observed data. Missing data will be handled using a mixed model repeated measures (MMRM) approach and will include terms for visit, treatment, treatment-by-visit interaction and randomization stratification factors as fixed effects and the corresponding baseline HbA1c value as a fixed effect covariate. Least squares mean treatment differences between the bexagliflozin group and the placebo group will be estimated from the model at week 24 with the corresponding p-values and their two-sided 95% CIs presented. An unstructured covariance will be used to model the within-subject correlation. In the unlikely event the model with the unstructured covariance structure does

not converge, an autoregressive (1) covariance structure will be used. HbA1c values obtained after the start of rescue medication will not be excluded from the analysis.

As a secondary sensitivity analysis, the multiple imputation method will be used to impute missing observations (including observations obtained after rescue medication) prior to carrying out the MMRM analysis. To further examine the sensitivity of the analysis, a last observation carried forward (LOCF) method will then be used to impute the missing observations prior to carrying out the MMRM model.

For supportive analyses, the primary efficacy endpoint will be analyzed with observed available data using the PP analysis sets in a similar manner as above.

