- b. After the non-monotone missing data have been imputed, the remaining monotone missing data will be imputed within each treatment arm and subgroup, defined by whether subject completed 24 week of study treatment, using regression approach. The predictors for the regression imputation model at any time point will be HbA_{1c} at all previous time points, including baseline. Imputations will be performed using a sequence of regression-based imputations (using PROC MI statement MONOTONE REG) at each post-baseline time point.
- c. Imputed data in each of the multiple imputed datasets will be analyzed using a mixed model repeated measures (MMRM) approach. The MMRM model will include treatment, visit, treatment-by-visit interaction, region, visit, treatment, treatment-by-visit interaction, baseline eGFR categories (<60 or ≥60 mL min⁻¹ per 1.73 m²), baseline BMI (< or ≥25 kg m⁻²), and history of heart failure (yes or no), insulin use or not, as fixed effects and the corresponding baseline HbA_{1c} as a fixed effect covariate. The analysis will evaluate the mean change from baseline in HbA_{1c} over the 24 week double blind treatment period. An unstructured covariance will be used to model the within subject correlation. The Kenward Roger approximation will be used to estimate denominator degrees of freedom. If the model with the unstructured covariance structure does not converge, an autoregressive(1) covariance structure will be used. HbA_{1c} values obtained after the start of intensification of hypoglycemic agent will not be excluded from the analysis. The treatment and treatment by visit interaction terms allow for comparisons of the treatment groups at each visit, and over week 6 to week 24. Least squares (LS) mean treatment differences between the bexagliflozin group and the placebo group at week 24 will be estimated from the model. The LS mean results from all imputed datasets will be combined using the Rubin's combination rule (PROC MIANALYZE).

If no sufficient week 24 values from treatment discontinued subjects are available for imputation, MMRM analysis will be performed using all available data. Method described in above step c will be utilized.

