8.2.1. Key secondary efficacy endpoints and analyses

A hierarchical testing procedure will be applied to these endpoints in the sequence of key secondary endpoints provided above. These key secondary endpoints will only be tested sequentially when significant treatment differences are established for the primary efficacy endpoint in the comparisons between the bexagliflozin and placebo groups.

Analysis for key secondary endpoints will be based on the ITT analysis set and repeated for the PP analysis set.

8.2.1.1. Change in HbA_{1c} from baseline to week 24 in randomized subjects who have been prescribed insulin to control their diabetes

This will be tested if the primary efficacy endpoint is significant. Change from baseline in HbA_{1c} at week 24 will be analyzed using the MMRM ANCOVA model with unstructured

covariance assumption. The model will include terms for treatment, baseline eGFR categories (<60 or ≥ 60 mL min⁻¹ per 1.73 m²), baseline BMI ($<$ or ≥ 25 kg m⁻²), and history of heart failure (yes or no), visit, treatment-by-visit interaction, and region as fixed effects and the corresponding baseline HbA_{1c} value as an additional fixed effect covariate. Data up to week 24 for subjects who have been prescribed insulin to control their diabetes will be used. Treatment comparison p-values and difference at week 24 will be estimated from the model, with the two-sided 95% CIs of the treatment difference also presented. If the model does not converge with the unstructured correlation assumption, an autoregressive AR(1) model will be used. If AR(1) does not converge, a compound symmetry model will be used.

Subgroup analysis will be conducted by baseline HbA_{1c} category and baseline eGFR categories.

8.2.1.2. Change in body weight from baseline to week 48 in subjects with BMI ≥ 25 kg m⁻²

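### The HbA1c MMRMs fit one baseline slope for all visits; a baseline-by-visit term costs almost nothing and may slightly tighten the week 24 comparison

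*Combined protocol and SAP*

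**What the plan says.** SAP 8.1.1 step c lists treatment, visit, treatment-by-visit, region, eGFR category, BMI category, heart failure history and insulin use, and then baseline HbA1c as a single covariate: "insulin use or not, as fixed effects and the corresponding baseline HbA_{1c} as a fixed effect covariate". On the covariance it says "An unstructured covariance will be used to model the within subject correlation". On the contrasts it says "The treatment and treatment by visit interaction terms allow for comparisons of the treatment groups at each visit". The tested contrast is the one at week 24.

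The first key secondary model (SAP 8.2.1.1, insulin subset) treats baseline in the same way: "as fixed effects and the corresponding baseline HbA_{1c} value as an additional fixed effect covariate". Protocol 9.5.1 agrees, with "randomization stratification factors as fixed effects and the corresponding baseline HbA1c value as a fixed effect covariate". No baseline-by-visit term appears in any of these places.

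The imputation in SAP 8.1.1 step b is more flexible: "The predictors for the regression imputation model at any time point will be HbA_{1c} at all previous time points, including baseline". A separate regression is fitted at each visit, so the baseline coefficient is free to differ by visit there. The analysis model in step c then applies one slope to the same data.

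**The concern.** Protocol 6.14 describes HbA1c as an average over two to three months. At week 6 that window still includes glucose from before randomization, so change from baseline may depend less on the baseline value then than at week 24. A single slope cannot follow such a shift. Under an unstructured covariance the common slope is weighted toward the visits with the smaller residual variance. These are usually the early ones, so week 24, the only visit tested, may be under-adjusted for baseline.

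Only precision is at stake. The week 24 standard error could be somewhat larger than necessary in the primary analysis and in the insulin subset, which is about half the size. The SAP gives no reason for restricting the slope in step c when step b leaves it free.

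**Working it through.** **1. The plan's power figures.** Protocol 9.2 and SAP 3.7 give N = 1650, 2:1 allocation (1100/550), effect 0.22%, SD 1.1% and 90% power. The protocol synopsis says "Statistical significance will be declared at a two-sided 0.05 level of significance"; SAP 6.1 uses one-sided 0.025, which has the same critical value.

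- Primary: SE = 1.1 × √(1/1100 + 1/550) = 0.0574. Then 0.22/0.0574 = 3.83, and power = Φ(3.83 − 1.96) = 96.9%. The stated 90% does not reproduce; it is conservative. With 6.5% loss, power is 95.9%.
- Insulin subset (800 subjects, 0.3%, SD 1.1%): SE = 1.1 × √(3/1600 + 3/800) = 0.0825. Power = Φ(3.64 − 1.96) = 95.3%, which agrees with the stated >90%.

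**2. Formula for the loss.** HbA1c is scheduled at weeks 6, 12 and 24, since "The interactions at week 2 and week 18 will be conducted by phone unless a clinic visit is necessary". With complete data, a full treatment-by-visit term and unstructured covariance, the week 24 estimate is

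(difference in mean change) − b × (difference in mean baseline).

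Under the SAP model b is the common slope, b = 1′S⁻¹β / 1′S⁻¹1, where β holds the visit-specific slopes and S is the residual covariance. With a baseline-by-visit term, b becomes β24. The ratio of week 24 variances, SAP model over extended model, is

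VR = 1 + (β24 − b)² × SDbase² / (residual variance at week 24).

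**3. Assumptions.** The documents supply only the entry range of 7.0 to 11%. I assumed baseline SD 0.9, a 12-week correlation of 0.6 to 0.9 with three forms of decay, and a week 24 SD of 1.0 to 1.3 times the baseline SD. That makes 6 × 3 × 4 = 72 patterns.

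**4. A case near the extreme.** Take all SDs as 0.9 and a correlation of 0.7 per 12 weeks, decaying as a power of time. The slopes at weeks 6, 12 and 24 are −0.16, −0.30 and −0.51. The residual SDs are 0.49, 0.64 and 0.78, and the GLS weights are 0.80, 0.04 and 0.16. So b ≈ −0.23, VR = 1 + (0.285² × 0.81)/0.6155 = 1.107, and the SE would fall by 1 − 1/√1.107 = 5.0%. In 3,000 simulated trials of 1650 subjects the ratio was 1.106.

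**5. All 72 patterns.**

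| | VR | SE reduction | Primary power, from 96.9% | Insulin-subset power, from 95.3% |
|---|---|---|---|---|
| Median | 1.006 | 0.3% | 97.0% | 95.4% |
| Upper quartile | 1.037 | 1.8% | 97.4% | 95.9% |
| Maximum | 1.113 | 5.2% | 98.1% | 97.0% |

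The power columns take SD 1.1 as the SD under the SAP model and divide it by √VR. Three quarters of the patterns give an SE reduction below 2%.

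**6. By slope gap alone.** With baseline SD 0.8 to 1.0 and residual SD 0.8 to 1.1, a gap |β24 − b| of 0.1 gives an SE reduction of 0.3 to 0.8%. A gap of 0.2 gives 1.0 to 3.0%, and a gap of 0.3 gives 2.3 to 6.4%.

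**7. Bias and cost.** Both models were unbiased in all four simulated settings. With equal slopes the simulated ratio was 0.999, so the extra term gained nothing. Two more parameters cost a factor of about 1638/1636 = 1.001 in variance.

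**The case against.** The strongest reply is that the single slope is valid, prespecified and the same in protocol and SAP, and that nothing in the documents shows the slope changing. That stands. The averaging property of HbA1c makes a change plausible but does not establish one. A reader might infer that the plan certainly gives up precision; the documents do not contain the slopes, SDs or correlations needed to say so.

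It is also fair that the practical stakes are small. The sample size was set by the MACE+ count, not by HbA1c precision, and power is already high. A reader might apply 11% inflation to 1650 and count about 180 subjects lost. The information lost would be 1650 × (1 − 1/1.11) ≈ 164 at that extreme, and 1650 × (1 − 1/1.006) ≈ 10 at the median. No design decision depends on either figure.

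The change is not strictly free. It touches two confirmatory models and departs from the protocol's model statement. The visit windows in SAP 6.4 also include a week 18 row, so unscheduled values mapped there would add a third, sparsely estimated slope.

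A reader might extend the point to the body weight and SBP models, which also lack the term. The averaging argument is specific to HbA1c, and no calculation here covers those endpoints. None of these replies gives a positive reason to keep the restriction in the HbA1c models.

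**Conclusion.** The point holds as a minor, conditional improvement. If the baseline slope steepens between week 6 and week 24, the models in SAP 8.1.1 and 8.2.1.1 yield a week 24 standard error that is slightly too large: typically by less than 2%, and by about 5% at the extreme of the patterns examined. If slopes are equal the loss is nil. These sizes rest wholly on assumed slopes, SDs and correlations.

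A reader might take the omission as a source of bias. With complete randomised data it is not, and the simulations agree. The insulin-subset model is fitted without the imputation step, so complete-data unbiasedness does not strictly cover it. The documents, however, give no information on dropout by baseline from which to claim a bias. The primary conclusion is unlikely to turn on this.

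**What to change.** Add a baseline HbA1c-by-visit interaction to the MMRMs in SAP 8.1.1 step c and 8.2.1.1 before unblinding, and list the change in SAP section 12. State which visits enter the model, so that stray week 18 values do not create a poorly estimated slope.

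The cost is two parameters with HbA1c at weeks 6, 12 and 24 (three if week 18 is kept), or roughly 0.1% of variance at N = 1650, plus the documentation. A matching term in the weight and SBP models is optional.

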8.1.2. Sensitivity Analyses

Randomized subjects who withdraw consent to participate in the study will not be replaced. The early termination rate is estimated to be 6.5% annually. To the extent possible, attempts will be made to minimize the amount of missing data through measures planned in the study conduct, but if data are missing for the primary endpoints and the first key secondary endpoint (change in HbA_{1c} for subjects who have been prescribed insulin), the number, timing, pattern, and reason for the missing value will be summarized. The reason for missing values will be evaluated to investigate possible implications of missing values for efficacy assessments. The dropout patterns will be assessed by Kaplan-Meier plots, if applicable, to assess whether they differ between treatment arms. If there are missing values for the primary and key secondary analysis, all observed data will be analyzed and data obtained after rescue will not be excluded.

To evaluate the impact from missing data and intensification of hypoglycemic agent, the following sensitivity analyses will be conducted:

- 1) Tipping point analysis will be conducted. Data after intensification of hypoglycemic agent will be considered as missing. Following steps will be followed:
 - a. Create monotone missing data as step a in section 8.1.1;
 - b. Regression approach under MAR will be used to generate complete datasets. The predictors for the regression imputation model at any time point will be region, baseline eGFR categories (<60 or ≥ 60 mL min⁻¹per 1.73 m²), baseline BMI category (< 25 kg m⁻² or ≥ 25 kg m⁻²), history of heart failure (yes or no), insulin use or not, and HbA_{1c} at all previous time points, including baseline. The first imputed values will be penalized or rewarded based on the treatment subject received:
 - Subjects in the bexagliflozin group: missing value will be analyzed assuming the treatment effect is worsened by $\delta 1$ (where $\delta = 0.1$ to 0.5, in step of 0.1) compared to the subjects who have no missing value in the reduction of HbA_{1c} value;

- Subjects in the placebo group: missing value will be analyzed assuming the treatment effect is better by δ_2 (where $\delta = 0$ to 0.5, in step of 0.1) compared to the subjects who have no missing value in the reduction of HbA_{1c} value;

The penalty or reward will not be applied to the values from later time points as these values are penalized or rewarded through regression on previous time points.

- c. Imputed datasets will be analyzed and results combined as step c in section 8.1.1.

For each combination of (δ_1 , δ_2), 100 imputed datasets will be obtained. These 25 combinations will be separately analyzed to explore under which condition where the null hypothesis can no longer having evidence to be rejected.

- 2) Furthermore, data that are missing or after intensification of hypoglycemic agent will be imputed using LOCF. All observed data and the imputed values will be analyzed using MMRM model. Model as specified in the primary analysis will be used.

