8.1.1. Primary Efficacy Analysis

Let $\mu_{\text{Bexagliflozin}}$ and μ_{PBO} represent the mean changes from baseline in HbA_{1c} at Week 24 for bexagliflozin and placebo arms, respectively. The following hypotheses will be tested:

$$H_0: \mu_{\text{bexagliflozin}} - \mu_{\text{placebo}} \geq 0$$

$$H_a: \mu_{\text{bexagliflozin}} - \mu_{\text{placebo}} < 0$$

Missing data will be imputed via multiple imputations, following which the MMRM will be repeated on the complete datasets with results combined across complete datasets using standard multiple imputations techniques; HbA_{1c} values collected after the start of intensification of hypoglycemic agent will not be excluded. A pattern-mixture model will be used to explore the impact of the missing data. Imputation will be conducted within each treatment arm and subgroup (treatment completer vs. treatment terminated early) under the assumption that non-adherent subjects with missing data will follow the same trajectory of non-adherent subjects with values observed. All efforts will be made to retain subjects in the study. If treatment is discontinued, subjects are encouraged to remain in the study and complete all scheduled visits, including final follow-up visit. However, with all efforts, insufficient values may be available for reliable imputation. This analysis will be performed only if at least 5 subjects in each treatment arm completed scheduled week 24 visit after treatment is stopped. This number is chosen to allow sufficient data to establish a regression model for imputation. For this analysis, the following three-step approach outlined below will be used:

- a. Non-monotone (intermediate visits) missing data will be imputed first using the Monte Carlo Markov Chain (MCMC) method under the MAR assumption in all treatment arms (using the MCMC statement in PROC MI). Multiple chains option

(CHAIN=MULTIPLE option in the MCMC statement of PROC MI) will be used. For the non-monotone imputation of the HbA_{1c} missing data, a multivariate normal model will be used including variables for the HbA_{1c} at baseline and all post-baseline visits within each treatment group. Five hundred imputed datasets will be generated.

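### SAP 8.1.2 tipping-point analysis: the printed delta ranges give 30 combinations, not 25, with no unshifted cell, and step b leaves treatment out of the imputation model

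*Combined protocol and SAP*

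**What the plan says.** The stated purpose of SAP 8.1.2 is "To evaluate the impact from missing data and intensification of hypoglycemic agent". Item 1 is the tipping-point analysis: "Tipping point analysis will be conducted. Data after intensification of hypoglycemic agent will be considered as missing". It has three steps.

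- Step a borrows the non-monotone imputation of 8.1.1, which is run within each treatment group.
- Step b fills the remaining gaps: "Regression approach under MAR will be used to generate complete datasets". Its predictors are region, eGFR category, BMI category, heart failure history, insulin use, and HbA1c at baseline and all earlier visits. The first imputed value is then shifted. For bexagliflozin the penalty (delta1) goes from 0.1 to 0.5, and for placebo the reward (delta2) goes from 0 to 0.5, both in steps of 0.1. Each combination gets 100 imputed datasets.
- Step c analyses and pools the datasets as in 8.1.1.

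On the size of the grid the SAP says: "These 25 combinations will be separately analyzed". Item 2 is the only other sensitivity analysis listed: "data that are missing or after intensification of hypoglycemic agent will be imputed using LOCF".

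SAP 8.2.1.4 applies the same procedure to the insulin key secondary endpoint.

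**The concern.** A tipping-point analysis reports how far the imputed values must be moved, from a stated starting point, before significance is lost. It therefore needs a defined grid, a visible starting point, and an imputation model that preserves the treatment contrast before any shift is added.

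Here the count and the printed ranges disagree, so the set of runs is not fixed. The starting point is not in the grid. The step b model, read as written, removes part of the treatment effect from the imputed values before delta is applied, so the delta printed on a cell would understate the departure that the cell tests. What is at stake is how the robustness result is read, not the primary result itself.

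**Working it through.** **Grid count.** Inputs: the two ranges, the step and the 100 datasets per combination, all from SAP 8.1.2. Levels = (upper - lower)/step + 1.

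- delta1: (0.5 - 0.1)/0.1 + 1 = 5
- delta2: (0.5 - 0)/0.1 + 1 = 6
- As printed: 5 x 6 = 30 combinations, 30 x 100 = 3,000 datasets
- Stated: 25 combinations, 2,500 datasets. This is reproduced only as 5 x 5, which needs delta2 to start at 0.1, against the printed range.
- Both deltas from 0: 6 x 6 = 36 combinations, 3,600 datasets

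On the printed ranges and on the 5 x 5 reading alike, delta1 is at least 0.1, so (0,0) is absent.

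**Step b, compared with its neighbours.**

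| Place | How treatment enters the regression imputation |
|---|---|
| SAP 8.1.1 | "Imputation will be conducted within each treatment arm and subgroup (treatment completer vs. treatment terminated early"; no treatment predictor is needed |
| SAP 8.2.1.4 step b (weight, SBP) | Treatment is in the predictor list |
| SAP 8.1.2 step b | Neither a by-arm statement nor a treatment predictor |

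**Size if step b is followed literally.** Inputs: planning effect 0.22 (protocol 9.2, SAP 3.7); early termination 6.5% a year (SAP 8.1.2); first post-baseline HbA1c at week 6 (SAP Table 4). Assumption: the imputed fraction f is the same in both arms.

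A subject first missing at week 6 has only baseline information. With no treatment term, the expected imputed values at weeks 6, 12 and 24 are the same in both arms for the same baseline, so the contrast among these subjects is 0. The overall difference becomes (1 - f) x 0.22 + f x 0, a loss of 0.22 x f. Subjects first missing later keep part of the contrast through their observed earlier values, so 0.22 x f is an upper bound.

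- Dropout by week 6: 1 - (1 - 0.065)^(6/52) = 0.77%; loss 0.22 x 0.0077 = 0.0017 points
- Dropout by week 24: 1 - (1 - 0.065)^(24/52) = 3.05%; loss at most 0.22 x 0.0305 = 0.0067 points
- Insulin subset, planning effect 0.30: at most 0.30 x 0.0305 = 0.0092 points
- Post-intensification values are also imputed here, and their share is not given. For an assumed f of 10% to 30%, the bound is 0.022 to 0.066 points.

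Per subject first missing at week 6, the loss of 0.22 exceeds two 0.1 steps of the grid.

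**Check by simulation**, with assumed inputs: effects of 0.25, 0.35 and 0.40 at weeks 6, 12 and 24, 2:1 allocation, values missing completely at random from week 6, between-subject SD 0.5, residual SD 0.6, no delta. With treatment in the regressions, the week-24 estimate stays between -0.398 and -0.401.

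| Imputed fraction | Estimate without treatment | -0.40 x (1 - f) |
|---|---|---|
| 3% | -0.387 | -0.388 |
| 10% | -0.360 | -0.360 |
| 20% | -0.319 | -0.320 |
| 30% | -0.281 | -0.280 |

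The bound formula and the simulation agree.

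**The case against.** The sponsor has fair replies.

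- **The missing (0,0) cell.** The declared goal is to find where the null is no longer rejected, and (0.1, 0) is in the printed grid. On planned dropout it differs from (0,0) by at most 0.1 x 0.0305 = 0.003 points. This stands as to size. It does not repair the count or supply the reference cell.
- **Step b may be meant by arm.** The deltas are defined arm by arm relative to subjects without missing values, step a runs within treatment group, and 8.1.1 step b also lists no treatment predictor because it runs within arm. This is plausible. But 8.1.1 says so explicitly and 8.1.2 does not, while 8.2.1.4 names treatment. Two programmers could produce different results from the same text.

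A reader might also infer more than the documents support.

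- **That the SAP has no unshifted observed-data result at all.** SAP 8.1.1 plans a per-protocol analysis on observed data, and 8.2.2.2 fits an observed-data model of HbA1c over time. What is absent is narrower: unshifted imputation with post-intensification values set to missing.
- **That a delta run on the retrieved-dropout datasets is a required analysis left out.** That imputation is itself conditional ("only if at least 5 subjects in each treatment arm completed scheduled week 24 visit"), and treating post-intensification values as missing is a declared and legitimate aim. Such a run is a preference. On dropout alone it would probably confirm robustness.
- **That the delta is wrongly applied, or capped too low at 0.5.** The SAP discloses the rule: "The penalty or reward will not be applied to the values from later time points". It explains that later values shift through the regression. How much carries to week 24, and whether the cap binds, depend on visit correlations and an imputed fraction that the documents do not give.

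**Conclusion.** Two specification errors stand. The printed ranges define 30 combinations, not 25, and exclude the unshifted cell. Step b, as written, carries no treatment information in its regression.

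If step b is run literally, every cell is biased toward the null. The direction is conservative. The size is at most 0.0067 points for the primary endpoint on planned dropout, assuming the 0.22 planning effect, 6.5% annual dropout at a constant rate, equal imputed fractions in the arms, and the worst case that all dropouts are first missing at week 6. It could be several times larger if many subjects are intensified, and the documents do not allow that to be settled. If step b is in fact run by arm, the second error is one of wording only.

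Both errors carry over to the insulin key secondary endpoint. The primary test does not use this analysis and is unaffected. Severity is minor.

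**What to change.** In SAP 8.1.2, start both deltas at 0, state 36 combinations (3,600 imputed datasets at 100 each), and report the (0,0) cell as the reference. In step b, state that imputation is done within treatment arm, or add treatment to the predictor list as 8.2.1.4 already does for weight and SBP. Because 8.2.1.4 takes the HbA1c procedure from 8.1.2 by reference, the correction reaches the insulin endpoint without further text.

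The cost is a small wording change and 3,600 - 3,000 = 600 more imputed datasets than the printed ranges imply (1,100 more than the stated count implies), again for the insulin subset. No new data are needed.
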